**Exploratory Objectives.**

- To determine the change in inhaler metrics in patients experiencing an AECOPD during study period.
- To determine the correlation of inhaler metrics (PIF, inhalation volume, number of inhalation events) with the Digihaler metric algorithm-triggered DAQ.
- To describe COPD-related health-care resource utilization (HRU):
  - Number of COPD exacerbations-associated hospitalizations
    - Proportion of patients with 30-day COPD-related hospital re-admission
  - Number of COPD exacerbations-associated emergency room visits
    - Proportion of patients with 30-day COPD-related emergency room re-admission
  - SABA utilization
- To describe patient treatment/device satisfaction/ease of use.
- To describe patient APP satisfaction/ease of use.

**4 STUDY DESIGN****4.1 OVERALL DESIGN**

This is a multisite, observational, 3-month pilot study of ProAir Digihaler use in 60 COPD patients at-risk for AECOPD. Participants will be recruited from two sites (Wake Forest University, N=30; University of North Carolina at Chapel Hill, N=30). All participants will have spirometry-confirmed COPD with an increased AECOPD risk (defined as two moderate or one severe AECOPD in the last 12 months).

Participants will be recruited from existing clinical pools at both sites including COPD registries, virtual and in-person outpatient clinics (routine or post-hospital discharge). Although this study will not be powered to make meaningful assessments of inhaler metric changes at the time of an AECOPD, we are permitting patients recently discharged for an AECOPD event to be enrolled, which will permit assessment of changes during the recovery phase as well as enrich for individuals more likely to have an AECOPD event during study.

In light of the COVID pandemic, this study is designed to be conducted entirely virtually to minimize any potential interruptions related to COVID. Both UNC and Wake Forest have experience conducting virtual studies with local IRB approval. Potentially eligible patients will be identified and screened for possible inclusion through existing registry review, virtual clinic visits or in-person visits.

Potentially eligible participants will be contacted, with the permission of their care providers, by study investigators or research coordinators and assessed for interest. Based on local IRB approval, they will either be mailed an informed consent (ICF) for phone review with the research coordinator or will complete verbal consent over the phone. After consenting, participants will be mailed the ProAir Digihaler (provided by Teva) The study coordinator will contact the participant to ensure set-up and correct usage.

Participants will then be asked to use the ProAir Digihaler as their primary mode of SABA therapy as they would in usual treatment and indicated in the product package insert and Instructions for Use. They will be provided a COPD Action Plan to ensure they have appropriate instructions to handle a possible AECOPD. They will answer a daily self-assessment asking "How are you feeling?" with responses provided on a Leikert scale on the DAQ App, as well as Digihaler metric algorithm-triggered DAQ on the DAQ app.

The participants will be contacted once per month to collect CAT score and self-reported average albuterol use over the preceding month. They will also be asked about any AECOPD events requiring treatment with antibiotics or steroids in the prior month. If there is evidence during the calls of clinical deterioration by self report or an abrupt increase in CAT by > 4 units patients will be advised to contact their primary care or COPD provider.

Participants will be enrolled for three months duration. In the event the participant has an AECOPD within two weeks of end of study, they will be followed for 14 days after AECOPD resolution. Total participant duration is three months (+21 days to account for 14 days in event of AECOPD and seven day window at end of study). In the event their ProAir Digihaler does not last three months, they will be prescribed another device (provided by Teva). Hospital admission during the course of the study will not prohibit continued participation.

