**Description of Study****Intervention:**

In light of the COVID pandemic, this study is designed to be conducted entirely virtually to minimize any potential interruptions related to COVID. After identification and consenting, participants will be mailed the ProAir Dihihaler (provided by Teva). The study coordinator will contact the participant to ensure set-up and correct usage. Participants will be asked to use the ProAir Dihihaler as their primary mode of SABA therapy as they would in usual treatment and indicated in the product package insert and Instructions for Use. They will be provided a COPD Action Plan to ensure they have appropriate instructions to handle a possible AECOPD. They will answer a daily self-assessment asking "How are you feeling?" with responses provided on a Leikert scale on the DAQ App, as well as Dihihaler metric algorithm-triggered DAQ on the DAQ app. The DAQ will collect yes/no responses to questions focused on change in respiratory symptoms, sleep disturbances, daily activity limitation, and anxiousness.. The participants will be contacted once per month to collect CAT score and self-reported average albuterol use over the preceding month. They will also be asked about any AECOPD events requiring treatment with antibiotics and/or steroids or hospitalization in the prior month. Participants will be enrolled for three months duration. All individuals will be provided three inhalers at enrollment. In the event their ProAir Dihihaler does not last three months, they will be prescribed another ProAir Dihihaler (provided by Teva).

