### 5.4 STRATEGIES FOR RECRUITMENT AND RETENTION

The target number of study participants is 60 adult subjects (N=30 at each site). We expect that all, or nearly all, subjects will be recruited within 12 months. Subjects participating in other observational studies will not be excluded from participation, as long as they meet all other inclusion criteria, but interventional pulmonary drug studies will not be concurrently allowed. Participants will be recruited from existing clinical pools at both sites including COPD registries, virtual and in-person outpatient clinics (routine or post-hospital discharge). Although this study will not be powered to make meaningful assessments of inhaler metric changes at the time of an AECOPD, the purposeful enrollment of patients recently discharged for an AECOPD event will permit assessment of changes during the recovery phase as well as enrich for individuals more likely to have an AECOPD event during study. Given the purposeful design of the study through an all virtual process, we do not anticipate impediments to recruitment in light of the dynamic COVID pandemic.

As this is a study of short duration that incorporates a medication already part of a patient's routine care, we anticipate that there will not be significant issues with retention. Monthly phone calls will occur to record interval medical history. Such contacts also reinforce study participation and retention. Additionally, the provision of the inhaled medication by the study sponsor will further facilitate participant retention during the study. The use of a completion fee (described below) further facilitates study retention.

Subjects will be reimbursed \$50 for completion of each of the three calls, along with a \$50 completion fee (Totaling \$200) as a means of compensating patients for their time on calls and completing study questionnaires. As this is an all virtual study, there will not be any reimbursements for travel.

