## 6 STUDY INTERVENTION

### 6.1 STUDY INTERVENTION(S) ADMINISTRATION

#### 6.1.1 STUDY INTERVENTION DESCRIPTION

Participants will be recruited from two sites (Wake Forest University, N=30; University of North Carolina at Chapel Hill, N=30). Participants will be recruited from existing clinical pools at both sites including COPD registries, virtual and in-person outpatient clinics (routine or post-hospital discharge).

In light of the COVID pandemic, this study is designed to be conducted entirely virtually to minimize any potential interruptions related to COVID. Both UNC and Wake Forest have experience conducting virtual studies with local IRB approval. Potentially eligible patients will be identified and screened for possible inclusion through existing registry review, virtual clinic visits or in-person visits.

Potentially eligible participants will be contacted, with the permission of their care providers, by study investigators or research coordinators and assessed for interest. Based on local IRB approval, they will either be mailed an informed consent (ICF) for phone review with the research coordinator or will complete verbal consent over the phone. After consenting, participants will be mailed the ProAir Digihaler (provided by Teva) The study coordinator will contact the participant to ensure set-up and correct usage. Patients will participate in a monthly call to capture CAT score, albuterol use recall and AECOPD events during study period.

Participants will then be asked to use the ProAir Digihaler as their primary mode of SABA therapy as they would in usual treatment and indicated in the product package insert and Instructions for Use. They will answer a daily self-assessment asking "How are you feeling?" with responses provided on a Leikert scale on the DAQ App, as well as Digihaler metric algorithm-triggered DAQ on the DAQ app. The DAQ will collect yes/no responses to questions focused on change in respiratory symptoms, sleep disturbances, daily activity limitation, recent AECOPD diagnosis and treatment, and anxiousness, as well as the Leikert "How are you feeling?" scale. The DAQ questionnaire will be triggered in the app based on an algorithm incorporating data from the digihaler metrics. The DAQ will be only deployed when indicated by the algorithm or on an ad-hoc basis by the patient (but not necessarily daily). They will be provided a COPD Action Plan to ensure they have appropriate instructions to handle a possible AECOPD.

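### The one-month look-back for AECOPD at each call does not match the allowed call intervals, so on-study time can go unasked or be asked about twice

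*Combined protocol and SAP*

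**What the plan says.** The AECOPD question is worded three times in the combined protocol and SAP, each time with a one-month look-back. Sections 4.1 and 6.1.1 read "They will also be asked about any AECOPD events requiring treatment with antibiotics or steroids in the prior month". The Synopsis (Description of Study Intervention) reads "They will also be asked about any AECOPD events requiring treatment with antibiotics and/or steroids or hospitalization in the prior month", which also names hospitalization.

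The Schedule of Activities (Section 1.3) places screening at day −21, the confirmatory call at day 0, and the phone visits at 30 ± 7, 60 ± 7 and 90 ± 21 days. Exacerbation history is listed at screening and at the three phone visits, but not at the confirmatory call. For the last visit, Section 4.1 explains only a later limit: "Total participant duration is three months (+21 days to account for 14 days in event of AECOPD and seven day window at end of study". The extension applies under a stated condition: "In the event the participant has an AECOPD within two weeks of end of study, they will be followed for 14 days after AECOPD resolution".

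Other passages are broader:
- Section 6.1.1: "Patients will participate in a monthly call to capture CAT score, albuterol use recall and AECOPD events during study period".
- Section 5.4: "Monthly phone calls will occur to record interval medical history".
- Section 8.3.4 collects adverse events by start date from consent until 24 hours after the last study day, with time of onset, and treats deterioration of a baseline condition as an adverse event.

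Section 8.1 names self-report as the source of the AECOPD outcome.

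**The concern.** A look-back of fixed length covers follow-up exactly once only if the calls are that same length apart. Here they need not be. When two calls are further apart than a month, the days just after the earlier call are outside both look-backs. When they are closer, some days are inside both, and an undated event may be reported twice.

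The outcomes exposed are the exploratory ones in Section 3: AECOPD on study, hospitalizations and emergency visits, and 30-day re-admission. The analysis in Section 9.4 of inhaler metrics in the 7 days around an AECOPD is also exposed. That analysis needs dated events, and a re-admission needs both events of the pair. Events will be few in 60 participants followed for three months. The device data around an unreported event would exist, but nobody would know to look at them.

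**Working it through.** **Inputs.** Call windows from Section 1.3: call 1 on days 23–37, call 2 on days 53–67, call 3 on days 69–111. The plan's own extension reproduces: 14 + 7 = 21 and 90 + 21 = 111. The look-back L is one month, taken as 30 days (assumption; 28 and 31 also tried).

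**Intervals** (earliest later call minus latest earlier call, up to latest minus earliest):
- Day 0 to call 1: 23 to 37 days.
- Calls 1 to 2: 53 − 37 = 16 to 67 − 23 = 44 days.
- Calls 2 to 3: 69 − 67 = 2 to 111 − 53 = 58 days. If the early limit for call 3 is 7 days (day 83), the minimum is 83 − 67 = 16.

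**Formulas.** Unasked days per interval = max(0, interval − L). Days asked twice, between successive calls = max(0, L − interval).

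**Extremes, L = 30.**
- Calls on days 37, 53 and 111 leave (37 − 30) + 0 + (58 − 30) = 7 + 28 = 35 days unasked.
- Calls 2 and 3 on days 67 and 69 share 30 − 2 = 28 days.
- Calls on days 30, 60 and 90 give zero for both.

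**Averages, L = 30, each allowed day equally likely (assumption).** With all three calls within ±7 days:
- Day 0 to call 1: (1 + 2 + … + 7)/15 = 28/15 = 1.87.
- Calls 1 to 2: the sum over k = 1 to 14 of k(15 − k)/225 = 560/225 = 2.49.
- Calls 2 to 3: also 2.49.
- Total: 1.87 + 2.49 + 2.49 = 6.8 days.

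Under the printed windows the last term becomes 5.6, and the unrounded total is 9.9 days. Listing all combinations gives:

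| Call 3 allowed on | Mean days unasked | Share of follow-up | Mean days asked twice | Most days unasked |
|---|---|---|---|---|
| Days 83–97 | 6.8 | 7.5% | 5.0 | 21 |
| Days 69–111 (as printed) | 9.9 | 10.3% | 8.1 | 35 |
| Days 83–111 | 12.6 | 12.5% | 3.8 | 35 |

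**Month length.** With L = 28 or 31, mean unasked time is 13.3 or 8.5 days under the printed windows, and 10.2 or 5.4 days with all calls within ±7.

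**Before Day 0.** If screening is on day −21, call 1 comes 23 + 21 = 44 to 37 + 21 = 58 days later. A 30-day look-back then leaves 14 to 28 days after screening unasked. Conversely, a call on day 23 reaches back to day −7.

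**Scale in events.** The documents give no on-study rate. Assuming 1 to 2 AECOPD per patient-year, in line with the entry criterion of one severe or two moderate events in 12 months, 60 × (1 to 2) × 90/365 = 14.8 to 29.6 events. The question as worded would not reach about 1.1 to 2.2 of them (7.5%) or 1.5 to 3.0 (10.3%).

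**The case against.** The strongest reply is that the monthly question is not the only route. Section 6.1.1 says the calls capture AECOPD during the study period, Section 5.4 speaks of interval history, and the exacerbation-history row in Section 1.3 has no time limit. Section 8.3.4 requires adverse events dated from consent, and the DAQ in Section 6.1.1 includes an item on recent AECOPD. A reader might infer from the one-month wording that events are certain to be lost or double-counted. The documents do not support that, since dated adverse event records could recover missed events and expose duplicates.

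This stands as far as it goes, but it does not close the point. The broader passages state an intent that the instruction for the AECOPD question contradicts. Adverse events are gathered mainly in the same calls. Section 8.3.1 excludes pre-existing conditions unless they worsen or become more frequent, and Section 8.3.2 does not make every hospitalization an SAE. The DAQ appears only when triggered or opened by the patient, and its description in the Synopsis and Section 2.1 omits the AECOPD item. No section says that these records feed or de-duplicate the self-reported outcome in Section 8.1.

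Four stronger readings should be set aside:
- **2 to 58 days for every interval.** This applies only to calls 2 and 3, and the 2-day end needs the −21 side of the last window, which the text does not explain.
- **The late end of call 3 for everyone.** Beyond the seven-day window, the call is late because of an AECOPD the site already knows about.
- **A missed call 2 that silently removes a month.** Calls on days 30 and 90 alone would leave 30 of 90 days unasked, and Section 9.3 would keep that participant. But Section 7.3 requires rescheduling within a week and repeated attempts at contact.
- **The index event counted as on-study.** Recently discharged patients may enrol, but the event, consent, mailing and device set-up would all have to fall within about a week, followed by an early call 1. Exacerbation history is also taken at screening.

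**Conclusion.** The point holds in a limited form. The stated look-back does not fit the allowed call intervals, and the plan does not say which record settles the AECOPD count. The most representative figure is 6.8 unasked days, because only participants with a late AECOPD should go beyond the seven-day window at call 3. The 9.9-day figure takes the printed windows at face value. Both assume a 30-day month and evenly spread call days; calls clustered near nominal dates would leave less. They measure time the question does not reach, not events known to be lost.

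A reader might infer that the main result is at risk. It is not: the primary PIF variability outcome and both secondary outcome measures in Section 9.4 use no AECOPD counts. Section 9.2 already says the study is not powered for changes at AECOPD. The change is worth making because it is cheap and these events are scarce.

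**What to change.** In the Synopsis and Sections 4.1 and 6.1.1, replace the one-month look-back for AECOPD with: since the last completed study contact at which AECOPD history was taken. At call 1, the period should start at screening/consent. Starting at Day 0 would leave the time since screening unasked and would conflict with the from-consent capture in Section 8.3.4. In addition:
- Record onset, treatment and hospitalization dates for each event.
- Flag events that start between consent and Day 0 as pre-device, and treat events before consent as history.
- State in Section 9.4 that AECOPD and resource-use counts are de-duplicated by date against adverse event and DAQ records.
- Use one wording in all three places, since only the Synopsis names hospitalization, and reconcile the ± 21 in Section 1.3 with the +21 in the text.
- Keep the four-week recall for the albuterol-use question.

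With dated reports, this leaves no day unasked or asked about twice for any allowed call dates. The cost is a line in the call script, a few date fields on the CRF and a sentence in Section 9.4, with no added calls. The downside is slightly longer recall when a call is late or missed.

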#### 4.2 END OF STUDY DEFINITION

A participant is considered to have completed the study if he or she has completed all phases of the study including the last phone visit shown in the Schedule of Activities (SoA), Section 1.3.

### 5 STUDY POPULATION

#### 5.1 INCLUSION CRITERIA

- Age >40 years old
- History of cigarette smoking >=10 pack-years
- Established COPD defined as physician diagnosis along with spirometry confirmation (post-BD FEV1/FVC<0.70) within the last two years and an FEV1 ≤80% predicted
- Regular albuterol use (defined as at least one puff weekly for each of the last four weeks)
- Currently non-hospitalized
- Medical records confirmed history of two moderate AECOPD (defined as use of antibiotic or steroids to treat clinical event consistent with AECOPD) or one severe AECOPD (defined as ED/hospital visit) in prior 12 months
- Access to smartphone, tablet or computer and internet
- Willingness to switch current rescue inhaler/device to ProAir Digihaler

#### 5.2 EXCLUSION CRITERIA

Subjects presenting with any of the following will not be included in the trial:

- Allergy or inability/contraindication to use Albuterol Sulfate
- Any condition that, in the opinion of the site investigator, would compromise the subject's ability to participate in the study

### 5.3 SCREEN FAILURES

Screen failures are defined as participants who consent to participate in the study but are not subsequently enrolled in the study. A minimal set of screen failure information is required to ensure transparent reporting of screen failure participants, to meet the Consolidated Standards of Reporting Trials (CONSORT) publishing requirements and to respond to queries from regulatory authorities. Minimal information includes demography, screen failure details, eligibility criteria, and any serious adverse event (SAE).

### 5.4 STRATEGIES FOR RECRUITMENT AND RETENTION

The target number of study participants is 60 adult subjects (N=30 at each site). We expect that all, or nearly all, subjects will be recruited within 12 months. Subjects participating in other observational studies will not be excluded from participation, as long as they meet all other inclusion criteria, but interventional pulmonary drug studies will not be concurrently allowed. Participants will be recruited from existing clinical pools at both sites including COPD registries, virtual and in-person outpatient clinics (routine or post-hospital discharge). Although this study will not be powered to make meaningful assessments of inhaler metric changes at the time of an AECOPD, the purposeful enrollment of patients recently discharged for an AECOPD event will permit assessment of changes during the recovery phase as well as enrich for individuals more likely to have an AECOPD event during study. Given the purposeful design of the study through an all virtual process, we do not anticipate impediments to recruitment in light of the dynamic COVID pandemic.

As this is a study of short duration that incorporates a medication already part of a patient's routine care, we anticipate that there will not be significant issues with retention. Monthly phone calls will occur to record interval medical history. Such contacts also reinforce study participation and retention. Additionally, the provision of the inhaled medication by the study sponsor will further facilitate participant retention during the study. The use of a completion fee (described below) further facilitates study retention.

Subjects will be reimbursed \$50 for completion of each of the three calls, along with a \$50 completion fee (Totaling \$200) as a means of compensating patients for their time on calls and completing study questionnaires. As this is an all virtual study, there will not be any reimbursements for travel.

## 6 STUDY INTERVENTION

### 6.1 STUDY INTERVENTION(S) ADMINISTRATION

#### 6.1.1 STUDY INTERVENTION DESCRIPTION

Participants will be recruited from two sites (Wake Forest University, N=30; University of North Carolina at Chapel Hill, N=30). Participants will be recruited from existing clinical pools at both sites including COPD registries, virtual and in-person outpatient clinics (routine or post-hospital discharge).

In light of the COVID pandemic, this study is designed to be conducted entirely virtually to minimize any potential interruptions related to COVID. Both UNC and Wake Forest have experience conducting virtual studies with local IRB approval. Potentially eligible patients will be identified and screened for possible inclusion through existing registry review, virtual clinic visits or in-person visits.

Potentially eligible participants will be contacted, with the permission of their care providers, by study investigators or research coordinators and assessed for interest. Based on local IRB approval, they will either be mailed an informed consent (ICF) for phone review with the research coordinator or will complete verbal consent over the phone. After consenting, participants will be mailed the ProAir Digihaler (provided by Teva) The study coordinator will contact the participant to ensure set-up and correct usage. Patients will participate in a monthly call to capture CAT score, albuterol use recall and AECOPD events during study period.

Participants will then be asked to use the ProAir Digihaler as their primary mode of SABA therapy as they would in usual treatment and indicated in the product package insert and Instructions for Use. They will answer a daily self-assessment asking "How are you feeling?" with responses provided on a Leikert scale on the DAQ App, as well as Digihaler metric algorithm-triggered DAQ on the DAQ app. The DAQ will collect yes/no responses to questions focused on change in respiratory symptoms, sleep disturbances, daily activity limitation, recent AECOPD diagnosis and treatment, and anxiousness, as well as the Leikert "How are you feeling?" scale. The DAQ questionnaire will be triggered in the app based on an algorithm incorporating data from the digihaler metrics. The DAQ will be only deployed when indicated by the algorithm or on an ad-hoc basis by the patient (but not necessarily daily). They will be provided a COPD Action Plan to ensure they have appropriate instructions to handle a possible AECOPD.

The participants will be contacted once per month to collect CAT score and self-reported average albuterol use over the preceding month. They will also be asked about any AECOPD events requiring treatment with antibiotics or steroids in the prior month.

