### 8.1 OUTCOME ASSESSMENTS

- Digihaler PIF: mean, median, standard deviation
- Digihaler Inspiratory volume: mean, median, standard deviation
- Digihaler Inhaler usage: count
- Self-reported inhaler usage: Average use over the preceding month
- COPD Assessment Test (CAT) questionnaire: Collected monthly
- Self-report of COPD exacerbation events on study
- Responses to daily self-assessment asking "How are you feeling?" on Leikert scale (mean, median, standard deviation, variability)
- Responses to DAQ on the DAQ app (cumulative score and individual domains mean, median, and standard deviation; variability of the responses and adherence to daily reporting)

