## 9 STATISTICAL CONSIDERATIONS

### 9.1 HYPOTHESIS

We hypothesize that inhaler metrics (PIF, inhalation volume, rescue inhaler use) will vary among COPD populations. We also hypothesize that increased albuterol use will positively correlate with worse daily Leikert scores, declining PIF, lower inhalation volume and higher CAT scores. We hypothesize that self-reported albuterol use will be lower than actual albuterol use captured by the DAQ app. We hypothesize that increased albuterol use will positively correlate with more symptomatic DAQ responses. The proposed study is designed to yield an initial exploration of the metrics captures by the Digihaler in a COPD population.

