Additional exploratory analysis will include linear regression (continuous) or negative binomial regression (count) of the clinical and demographic factors associated with inhaler from primary and secondary outcomes; descriptive statistics (mean, median, variance estimate and 95% confidence intervals) of number of inhalation events, correlation of inhaler metrics (PIF, inhalation volume, number of inhalation events) with CAT score, correlation of inhaler metrics (PIF, inhalation volume, number of inhalation events) with daily self-assessment asking “How are you feeling?” with responses provided on a Leikert scale, correlation of inhaler metrics (PIF, inhalation volume, number of inhalation events) with responses to metric algorithm-triggered DAQ; change in inhaler metrics (during the 7 days after and/or leading into hospitalized AECOPD or home treatment of a moderate AECOPD defined by a prescription for steroids and/or antibiotics); descriptive statistics (proportion, 95% CI) of COPD-associated hospitalizations and emergency room visits as well as SABA utilization; and patient satisfaction will be assessed with a post-study survey. The Leikert scale will be modeled using an ordinal scale with lower number signifying worse daily overall feeling. The DAQ will be comprised of yes/no responses to a set of questions (categorized as No=0; Yes=1) with higher score calculated in the analysis indicating worse symptoms. In exploratory analyses, individual DAQ domains and cumulative score will be evaluated as outcomes. Because the DAQ also includes the Leikert scale, on days where both the DAQ Leikert and daily Leikert are completed, the DAQ Leikert will be used for analysis.

---

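### The DAQ is observed only when the Digihaler metrics trigger it or the patient opens it, so its planned correlation with those metrics is selected, and a daily adherence measure does not fit it

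*Combined protocol and SAP*

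**What the plan says.** **When a DAQ exists.** Section 6.1.1: "The DAQ questionnaire will be triggered in the app based on an algorithm incorporating data from the digihaler metrics". The next sentence reads "The DAQ will be only deployed when indicated by the algorithm or on an ad-hoc basis by the patient", and adds that this need not be every day. No trigger threshold, direction or expected frequency is given.

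**What is done with it.** Section 9.4 lists "correlation of inhaler metrics (PIF, inhalation volume, number of inhalation events) with responses to metric algorithm-triggered DAQ" among the exploratory analyses, matching an exploratory objective in Section 3. Section 9.1 states the expected sign: "We hypothesize that increased albuterol use will positively correlate with more symptomatic DAQ responses". No coefficient, unit of analysis or handling of days without a DAQ is given for this correlation. Section 9.3 says only that missing data are not imputed.

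**Adherence.** The DAQ bullet in Section 8.1 includes "variability of the responses and adherence to daily reporting". The daily Likert question has its own bullet, with no adherence measure.

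**Score.** Section 9.4 codes each yes/no answer 1 or 0, treats a higher total as worse symptoms, and evaluates single domains and a cumulative score. Section 6.1.1 includes among the DAQ topics "recent AECOPD diagnosis and treatment, and anxiousness". The Synopsis (description of study intervention) and Section 2.1 give four topics and omit the AECOPD item.

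**Likert.** The DAQ also contains the Likert question. Section 9.4 uses the DAQ version whenever both versions were answered on the same day.

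**The concern.** One variable in the correlation helps decide whether the other is recorded. If only triggered DAQs are used, the metric is confined to the part of its range that fires the algorithm, which weakens any correlation. Patient-initiated entries are a second way in, and patients may well make them on bad days. Pooling the two then selects days with either an unusual metric or bad symptoms. Among such days, those with an ordinary metric tend to be the symptomatic ones, which pushes the correlation downward.

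At stake is whether the study gives a fair first reading of how inhaler metrics relate to symptoms, which the Synopsis presents as groundwork for multicenter trials. Two further measures are affected. Daily adherence would penalise patients for days on which nothing was asked of them. A yes to an AECOPD diagnosis or treatment item could count as a worse symptom.

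**Working it through.** The plan states no expected correlation, trigger rate or ad-hoc rate, so there is no figure to reproduce. All rates and correlations below are assumptions, used to show direction and range.

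**1. Triggered DAQs only.** Let X be the standardised metric (higher means more albuterol use) and S the symptom level, bivariate normal with correlation 0.3. Suppose the trigger fires on the top 10% of X.
- Cut-off c = 1.2816; λ = φ(c)/0.10 = 1.755.
- Variance of X above the cut-off: v = 1 + cλ − λ² = 1 + 2.249 − 3.080 = 0.169.
- Correlation on triggered days: ρ√v / √(1 − ρ² + ρ²v) = 0.3 × 0.411 / √(0.91 + 0.015) = 0.123 / 0.962 = **0.13**.

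The result is attenuated and keeps its sign. A version closer to the instrument uses a count of five yes/no items and Spearman correlation. There, an all-day value of 0.24 falls to 0.09–0.11 when the trigger fires on 5–20% of days.

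**2. Triggered and patient-initiated DAQs pooled.** In the bivariate normal model, adding an ad-hoc entry on every day in the top 5% of symptoms gives about **-0.46**. In the five-item version (all-day value 0.24):

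| Ad-hoc opening | Trigger rate | Ad-hoc rate | Pooled correlation |
|---|---|---|---|
| Sharp symptom cut-off | 10% | 1% / 2% / 5% / 10% | -0.08 / -0.21 / -0.41 / -0.46 |
| Graded with symptoms (logistic slope 1 or 2 per SD) | 5–20% | 2% or 5% | -0.26 to +0.06 |
| Unrelated to symptoms | 5–20% | 2% or 5% | +0.15 to +0.30 |

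With a true 0.5 (all-day value 0.40), trigger on 10% of days and a sharp symptom cut-off, the first row becomes +0.05 / -0.07 / -0.26 / -0.31. With a true 0.7 the pooled value is mostly positive.

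**3. Allowing for patients.** The runs above treat days as independent. A further check used 90 days per patient, within- and between-patient correlations of 0.3, and trigger (10%) and ad-hoc (1–5%) rules relative to each patient's own baseline. The pooled day-level value depends on the share of variance between patients:
- 30% share: 0.00 to -0.22
- 50% share: +0.09 to -0.06
- 70% share: +0.09 to +0.17

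Correlating patient means stayed positive, +0.16 to +0.31. The unit of analysis, which Section 9.4 does not state, therefore matters as well.

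**4. Adherence.** Take a patient who answers every prompt over 90 days, with the trigger firing on 5%, 10% or 20% of days. That is 4.5, 9 or 18 DAQs. Divided by 90 days, adherence is 5%, 10% or 20%. Divided by DAQs triggered, it is 100%.

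**5. Unselected comparison.** In the same simulations a Likert answered on all days gave 0.24 at a true 0.3, the all-day value. The substitution rule in Section 9.4 would exchange that answer for the DAQ one on exactly the days chosen by the trigger or the patient.

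**The case against.** The strongest reply is that the plan never says it pools. The objective and the analysis both name the algorithm-triggered DAQ; patient-initiated entries appear only where deployment is described. Read literally, only triggered DAQs enter, and the result is attenuation without a sign change. This stands as far as it goes, and it is why sign reversal cannot be the main claim. It does not settle the matter: the phrase may simply name the instrument, no sentence excludes patient-initiated entries, and Sections 8.1 and 9.4 otherwise summarise DAQ responses without distinction.

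A reader might infer that the planned correlation will come out negative, or that the Section 9.1 hypothesis will be rejected by sampling alone. The documents support neither. Reversal needs pooling and symptom-driven ad-hoc entries at a material rate, and the most negative values rest on sharp cut-offs and independent days. No test or alpha is specified, so nothing is formally rejected.

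It is also fair that correlating the metrics with the daily Likert is already a secondary objective, so a better estimate is largely planned; that the Likert sits in the same app, so the daily adherence wording may merely be misplaced; and that Section 9.4 does not list the items in the cumulative score, while the shorter topic lists may be summaries. These points make the remedies clarifications, but the conflict between Sections 6.1.1 and 8.1 remains.

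**Conclusion.** The point holds in a limited form and should be corrected. Selection of DAQ days by the metrics is built into Section 6.1.1. If triggering restricts the metric's range, as assumed here, the triggered correlation understates the overall relation: about 0.13 for a true 0.3 with a trigger on the top 10% of days. Pooling symptom-driven patient-initiated entries would bias it further downward, from about -0.46 to slightly positive at the same true value. Where the study would fall depends on rates that the documents do not give. The adherence conflict needs no model, although its size (5–20% against 100%) depends on the assumed trigger rate. The AECOPD item is a secondary point about inconsistent lists and an unspecified score.

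The DAQ correlation is exploratory in a pilot without power calculations. The primary PIF outcome does not use the DAQ and is unaffected.

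**What to change.** 1. **Section 9.4, DAQ correlation.** Flag each DAQ as triggered or patient-initiated, analyse the two separately, and report the triggered result as conditional on a trigger. State the trigger rule, the coefficient and the unit of analysis. Section 6.1.1 mentions back-end data extracts but not this field, so confirm that it exists.
2. **Section 9.4, Likert.** Name the planned daily Likert correlation as the estimate of the overall metric-symptom relation. For that analysis, keep the daily answer and do not replace it with the DAQ Likert.
3. **Section 8.1.** Define DAQ adherence as DAQs completed divided by DAQs triggered, count patient-initiated entries separately, and apply daily adherence to the Likert item.
4. **Item lists and score.** Reconcile the DAQ topics in the Synopsis, Section 2.1 and Section 6.1.1. Report the cumulative symptom score without the AECOPD diagnosis/treatment item, and show that item on its own.

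The cost is wording and one data field, with no new prompts to patients. The downside is fewer DAQs in each separate analysis.
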